## HMPL-523

			ATOXGR			
PARAM (SI Unit)	Hypo	Hyper	GRADE 1	GRADE 2	GRADE 3	GRADE 4
Glucose (mmol/L)	Hypoglycemia		<LLN - 55 mg/dL; <LLN - 3.0 mmol/L	<55 - 40 mg/dL; <3.0 - 2.2 mmol/L	<40 - 30 mg/dL; <2.2 - 1.7 mmol/L	<30 mg/dL; <1.7 mmol/L
Creatinine (umol/L)		Creatinine increased	>ULN - 1.5 x ULN	>1.5 - 3.0 x baseline if baseline was abnormal; >1.5 - 3.0 x ULN if baseline was normal	>3.0 x baseline-6.0xULN if baseline was abnormal; >3.0 - 6.0 x ULN if baseline is normal	>6.0 x ULN
Creatine Kinase (IU/L)		CPK increased	>ULN - 2.5 x ULN	>2.5 x ULN- 5 x ULN	>5.0 X ULN - 10.0 x ULN	>10.0 x ULN
Alkaline Phosphatase (IU/L)		Alkaline phosphatase increased	>ULN - 2.5 x ULN if baseline was normal; [a] 2.0 - 2.5 x baseline if baseline was abnormal [b]	>2.5 - 5.0 x ULN if baseline was normal; [a] >2.5 - 5.0 x baseline if baseline was abnormal [b]	>5.0 - 20.0 x ULN if baseline was normal; [a] >5.0 - 20.0 x baseline if baseline was abnormal [b]	>20.0 x ULN if baseline was normal; [a] >20.0 x baseline if baseline was abnormal [b]
Aspartate Aminotransferase (IU/L)		Aspartate aminotransferase increased	>ULN - 3.0 x ULN if baseline was normal; [a] 1.5 - 3.0 x baseline if baseline was abnormal [b]	>3.0 - 5.0 x ULN if baseline was normal; [a] >3.0 - 5.0 x baseline if baseline was abnormal [b]	>5.0 - 20.0 x ULN if baseline was normal; [a] >5.0 - 20.0 x baseline if baseline was abnormal [b]	>20.0 x ULN if baseline was normal; [a] >20.0 x baseline if baseline was abnormal [b]
Alanine Aminotransferase (IU/L)		Alanine aminotransferase increased	>ULN - 3.0 x ULN if baseline was normal; [a] 1.5 - 3.0 x baseline if baseline was abnormal [b]	>3.0 - 5.0 x ULN if baseline was normal; [a] >3.0 - 5.0 x baseline if baseline was abnormal [b]	>5.0 - 20.0 x ULN if baseline was normal; [a] >5.0 - 20.0 x baseline if baseline was abnormal [b]	>20.0 x ULN if baseline was normal; [a] >20.0 x baseline if baseline was abnormal [b]

HUTCHMED Ltd.

CONFIDENTIAL

## HMPL-523

			ATOXGR			
PARAM (SI Unit)	Hypo	Hyper	GRADE 1	GRADE 2	GRADE 3	GRADE 4
Calcium (mmol/L)	Hypocalcemia	Hypercalcemia	>ULN - 2.9 mmol/L	>2.9 - 3.1 mmol/L	>3.1 - 3.4 mmol/L	>3.4 mmol/L
			<LLN - 2.0 mmol/L	<2.0 - 1.75 mmol/L	<1.75 - 1.5 mmol/L	<1.5 mmol/L
Magnesium (mmol/L)	Hypomagnesemia	Hypermagnesemia	>ULN - 3.0 mg/dL; >ULN - 1.23 mmol/L	~	>3.0 - 8.0 mg/dL; >1.23 - 3.30 mmol/L	>8.0 mg/dL; >3.30 mmol/L
			<LLN - 1.2 mg/dL; <LLN - 0.5 mmol/L	<1.2 - 0.9 mg/dL; <0.5 - 0.4 mmol/L	<0.9 - 0.7 mg/dL; <0.4 - 0.3 mmol/L	<0.7 mg/dL; <0.3 mmol/L
Potassium (mmol/L)	Hypokalemia	Hyperkalemia	>ULN - 5.5 mmol/L	>5.5 - 6.0 mmol/L	>6.0 - 7.0 mmol/L	>7.0 mmol/L
			<LLN - 3.0 mmol/L	~	<3.0 - 2.5 mmol/L	<2.5 mmol/L
Cholesterol (mmol/L)		Cholesterol high	>ULN - 300 mg/dL; >ULN - 7.75 mmol/L	>300 - 400 mg/dL; >7.75 - 10.34 mmol/L	>400 - 500 mg/dL; >10.34 - 12.92 mmol/L	>500 mg/dL; >12.92 mmol/L
Bilirubin (umol/L)		Blood bilirubin increased	>ULN - 1.5 x ULN if baseline was normal; [a] > 1.0 - 1.5 x baseline if baseline was abnormal [b]	>1.5 - 3.0 x ULN if baseline was normal; [a] >1.5 - 3.0 x baseline if baseline was abnormal [b]	>3.0 - 10.0 x ULN if baseline was normal; [a] >3.0 - 10.0 x baseline if baseline was abnormal [b]	>10.0 x ULN if baseline was normal; [a] >10.0 x baseline if baseline was abnormal [b]
Triglycerides (mmol/L)		Hypertriglyceridemia	150 mg/dL - 300 mg/dL; 1.71 mmol/L - 3.42 mmol/L	>300 mg/dL - 500 mg/dL; >3.42 mmol/L - 5.7 mmol/L	>500 mg/dL - 1000 mg/dL; >5.7 mmol/L - 11.4 mmol/L	>1000 mg/dL; >11.4 mmol/L
Urine Protein		Proteinuria	1+ proteinuria; urinary protein $\geq$ ULN - <1.0 g/24 hrs	2+ and 3+ proteinuria; urinary protein 1.0- <3.5g/24hrs	4+ proteinuria; urinary protein $\geq$ 3.5g/24hrs	~

## HMPL-523

PARAM (SI Unit)	Hypo	Hyper	ATOXGR			
			GRADE 1	GRADE 2	GRADE 3	GRADE 4
Lactate Dehydrogenase (IU/L)		Blood lactate dehydrogenase increased	>ULN	~	~	~
Gamma Glutamyl Transferase (IU/L)		GGT increased	>ULN - 2.5 x ULN if baseline was normal; [a] 2.0 - 2.5 x baseline if baseline was abnormal [b]	>2.5 - 5.0 x ULN if baseline was normal; [a] >2.5 - 5.0 x baseline if baseline was abnormal [b]	>5.0 - 20.0 x ULN if baseline was normal; [a] >5.0 - 20.0 x baseline if baseline was abnormal [b]	>20.0 x ULN if baseline was normal; [a] >20.0 x baseline if baseline was abnormal [b]
Urate (umol/L)		Hyperuricemia	>ULN	~	~	~
pH	Acidosis	Alkalosis	pH >normal, but <=7.5	~	pH >7.5	~
			pH <normal, but >=7.3	~	pH <7.3	~
Leukocytes (10  /L)	White blood cell decreased	Leukocytosis	~	~	>100,000/mm 	~
			<LLN - 3000/mm  ; <LLN - 3.0 x 10e9 /L	<3000 - 2000/mm  ; <3.0 - 2.0 x 10e9 /L	<2000 - 1000/mm  ; <2.0 - 1.0 x 10e9 /L	<1000/mm  ; <1.0 x 10e9 /L

LLN = Lower limit of normal, ULN = Upper limit of normal; ~ = Not applicable

[a] If the baseline value is normal, the toxicity grade will be determined by the post-baseline value and the ULN (e.g., > ULN - 2.5 x ULN).

[b] If the baseline value is abnormal, the toxicity grade will be determined by the baseline value and the post-baseline value (e.g., 2.0 - 2.5 x baseline). This rule only applies to the abnormal baseline value that is higher than the normal range upper limit.

HMPL-523

---

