Statistical Methods	
Determination of Sample Size
 
The study is closed to new enrollment; the last patient was enrolled on CCI. The total number of patients enrolled in the dose-expansion

	
phase of the study at the time of enrollment closure is 48, with 3 patients continuing on treatment.
 
The sample size rationale for the study prior to closing for further enrollment is described below.
 
Stage 1: Dose Escalation
 
The sample size for Stage 1 is based on the dose-escalation rules of the 3 + 3 design. For a given AE with a true rate of 10%, 5%, or 1%, the probability of observing at least 1 such AE in a given cohort of 6 patients is 46.9%, 26.5%, and 5.8%, respectively.
 
Stage 2: Dose Expansion
 
The planned enrollment for Stage 2 was approximately 70 patients. A total of 70 patients will provide more robust safety data in the patient populations studied. For a given AE with a true rate of 10%, 5%, or 1%, the probability of observing at least 1 such AE in 70 patients is 99.9%, 97.2%, and 50.5%, respectively.

Safety Analysis
	
Data will be summarized by dose level, subtype of malignancy, and overall, as appropriate. The DLTs will be listed. The incidence of TEAEs, SAEs, AEs of special interest, and AEs leading to dose interruption, reduction, or treatment discontinuation will be presented by Medical Dictionary for Regulatory Activities System Organ Class and preferred term, by relationship to study drug, by toxicity grade, and by severity for each dose level, and by type of malignancy. For laboratory tests that are graded by NCI CTCAE v5.0 or higher, results will be summarized by grade. Descriptive statistics for vital signs and 12-lead electrocardiogram parameters will be presented by dose level and visit and also by type of malignancy and visit. Physical examinations findings will be listed.

Pharmacokinetic Analysis
	
A noncompartmental model analysis will be performed for plasma concentration data by a central laboratory using Phoenix WinNonlin. Individual and mean plasma concentration of HMPL-523 and CCI [REDACTED] versus time data will be tabulated and presented. Descriptive statistics (n, mean, standard deviation, minimum, median, maximum, geometric mean, and coefficient of variation) for all of the relevant PK parameters of HMPL-523 and CCI [REDACTED] will be presented.

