A total of 51 TEAEs were reported during the study by 19 subjects (79.2%) who received HMPL-523, and 10 TEAEs were reported by 6 subjects (75.0%) who received placebo. Two DLTs were observed and reported as SAEs. These were 1 elevated lipase (200-mg cohort) and 1 pyrexia (400-mg cohort). The majority of TEAEs reported in the HMPL-523 treatment groups were mild in intensity. A total of 12 events reported by 8 subjects were moderate in intensity, and SAEs that were determined to be DLTs were considered severe in intensity. Three TEAEs (elevated lipase, pyrexia, and elevated alanine aminotransferase [ALT]) reported by 3 subjects were considered probably related to HMPL-523; 29 TEAEs reported by 15 subjects were considered possibly related to HMPL-523. TEAEs reported by more than 1 subject who received HMPL-523 included headaches (n = 11), increased ALT (n = 5), dizziness (n = 3), malaise (n = 3), upper respiratory tract infections (n = 3), increased lipase (n = 2), somnolence (n = 2), lethargy (n = 2), constipation (n = 2), and back pain (n = 2).

Part C

A total of 6 subjects (1 cohort) were enrolled in Part C and received a single dose of HMPL-523 100 mg under fasted conditions (Period 1). Following a washout period of 7 days, each subject received a single dose of HMPL-523 100 mg with a high-fat meal (Period 2). All subjects completed the study as planned.

A total of 4 subjects (66.7%) reported TEAEs after receiving a single dose of HMPL-523 under fasted conditions. No DLTs or SAEs were observed. TEAEs reported by at least one subject include pain in extremity (n = 2), plantar fasciitis (n = 1), and cough (n = 1). Three TEAEs (2 pains in extremity and 1 plantar fasciitis) were mild in intensity, and 1 TEAE (cough) was moderate in intensity. All TEAEs were considered to be not related to HMPL-523.

Pharmacokinetics

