4.8.2 Secondary Safety Outcome Measures

- Incidence of TEAEs by NCI CTCAE v5.0 grade and associated dose of HMPL-523
- Incidence of Grade 3 and 4 abnormalities in safety-related laboratory parameters and associated dose of HMPL-523
- Incidence of TEAEs leading to HMPL-523 dose interruption, reduction, or treatment discontinuation

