- Viral serology should be tested at screening and include the following:

- HIV
- HBV (HBsAg and HBcAb; also HBsAb and HBV DNA by PCR if the patient is HBcAb positive)
- HCV (HCV antibody; also, HCV RNA by PCR if the patient is HCV antibody positive)
- CMV (CMV antibody; also, CMV DNA by PCR if the patient is CMV antibody positive)
- Urinalysis or dipstick (pH, specific gravity, glucose, protein, ketones, and blood), should be tested at screening (preferably within 7 days prior to the first dose of the investigational medicine); Day 15 of Cycle 1; Days 1 and 15 of Cycle 2; Day 1 of every cycle from Cycle 3 onwards; and at study completion or early termination. If protein $\geq 2+$ during the period of study treatment, a 24-hour urine test should be conducted within 1 week.
- Leukocyte immunophenotyping (fluorescence-activated cell sorting subsets) should be done at screening (preferably within 7 days prior to the first dose of the investigational medicine), Day 15 of Cycle 1, and Day 1 of Cycle 2, which includes:
 - Determination of T lymphocyte/B lymphocyte/natural killer cell counts (CD3, CD19, CD4, CD8, and CD16/56) using a standard cell marker panel.
 - Patients with CLL: 17p del/TP53 mutation status at screening (optional).As of Amendment 5, leukocyte immunophenotyping will not be performed from Cycle 3 onwards.
- All women who are not postmenopausal (no menses for at least 1 year without alternative medical cause) will have a serum β -HCG test at screening and study completion or early termination.
- WM/LPL related testing:
 - Serum immunoglobulins assessment (quantitative immunoglobulin assessment of IgM, IgA, and IgG) will be performed for patients with WM/LPL at screening (preferably within 7 days prior to the first dose of the investigational medicine), Day 1 of every cycle from Cycle 2 onwards, study completion or early termination, quarterly during the follow-up period, and at the time of CR confirmation.

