7.3.3.3 Clinical Laboratory Test Values

Descriptive statistics for each clinical laboratory test will be presented for each dose level and scheduled visit in the dose escalation stage and also by type of malignancy in the dose expansion stage. Laboratory test values from the hematology and chemistry panels, which can be graded by NCI CTCAE, will be summarized by the shift of NCI CTCAE grade from baseline to the highest grade reported during the study.

Selected laboratory tests may be plotted over time for each patient.

All laboratory test results will be listed.

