### 17.4. LABORATORY EVALUATIONS

The following laboratory evaluations will be summarized in tables:

- Chemistry
- Coagulation
- Fasting lipid profile
- Hematology
- Leukocyte immunophenotyping
- Serum immunoglobulin
- Serum amylase and lipase
- Serum  $\beta$ -2 microglobulin
- Urinalysis

The following laboratory evaluations will be listed in listings:

- Chemistry
- Coagulation
- Fasting lipid profile

HMPL-523

- 
- Hematology
  - Leukocyte immunophenotyping
  - Serum immunoglobulin
  - Serum amylase and lipase
  - Serum  $\beta$ -2 microglobulin
  - Urinalysis
  - Pregnancy test
  - Viral serology

Quantitative laboratory measurements reported as “< X”, i.e. below the lower limit of quantification (LLQ), or “> X”, i.e. above the upper limit of quantification (ULQ), will be converted to X for the purpose of quantitative summaries, but will be presented as recorded, i.e. as “< X” or “> X” in the listings.

Descriptive statistics for all quantitative laboratory evaluations and change from the baseline will be presented in SI units for each visit.

For laboratory parameters graded by NCI CTCAE, version 5.0 (see [Appendix 2](#)), changes in CTC grade laboratory data will be summarized as shift table from baseline to worst post-baseline grade. Baseline CTCAE grade is derived from the last laboratory assessment prior to the first administration of study medication, as defined in [section 7.2](#). Worst (maximum) post-baseline CTCAE grade is derived with all measurements from the first dose administration of study medication to no more than 37 days after the last dose of study medication or new anti-cancer therapies, which comes earlier. Otherwise, the shift table will be presented by ‘normal’, ‘abnormal but not clinically significant’, ‘abnormal and clinically significant’.

All CTCAE Grade 1 or higher abnormalities in laboratory tests will be flagged in the listings.

The incidence of patients with the following abnormal liver function tests (Hy’s Law) at any time post baseline will also be summarized:

HMPL-523

- ALT or AST  $\geq 3$  x ULN and  $\leq 5$  x ULN
- ALT or AST  $\geq 5$  x ULN
- Total bilirubin  $\geq 2$  x ULN
- (ALT or AST  $\geq 3$  x ULN) and total bilirubin  $\geq 2$  x ULN
- (AST or ALT  $\geq 3$  x ULN) and total bilirubin  $\geq 2$  x ULN and ALP  $< 2$  x ULN

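### SAP Appendix 2 has no CTCAE grading rows for serum lipase, serum amylase or sodium, so their laboratory Grade 3/4 incidence would go unreported; its pH row fits no scheduled blood test

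*SAP*

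**What the plan says.** **The outcome.** Protocol 4.8.2 names as a secondary safety outcome "Incidence of Grade 3 and 4 abnormalities in safety-related laboratory parameters and associated dose of HMPL-523". The synopsis (Safety Analysis) states a broad reporting rule: "For laboratory tests that are graded by NCI CTCAE v5.0 or higher, results will be summarized by grade". Protocol 7.3.3.3 is narrower and applies the grade shift to "Laboratory test values from the hematology and chemistry panels, which can be graded by NCI CTCAE".

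**The data.** Protocol 5.6.9 places sodium in the chemistry panel and lists serum amylase and lipase as a separate item. Both are drawn at screening, Days 8, 15 and 22 of Cycle 1, Days 1 and 15 of Cycle 2, Day 1 of each later cycle, and study completion or early termination. pH appears once, under "Urinalysis or dipstick (pH, specific gravity, glucose, protein, ketones, and blood".

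**The analysis.** SAP 17.4 says that, for parameters graded by CTCAE version 5.0, with a pointer to Appendix 2, "changes in CTC grade laboratory data will be summarized as shift table from baseline to worst post-baseline grade". For the rest: "Otherwise, the shift table will be presented by" three categories, namely normal and abnormal with or without clinical significance. SAP 17.4 also flags results of Grade 1 or above in the listings.

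**The grading table.** SAP Appendix 2 has a pH row labelled acidosis and alkalosis. Its Grade 1 acidosis entry is "pH <normal, but >=7.3". Values below 7.3, or above 7.5 on the alkalosis side, are Grade 3. No specimen is named.

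**The concern.** A graded laboratory summary can cover only the analytes that have a grading rule. Three analytes that are collected throughout have none, so the Grade 3/4 outcome would be incomplete without the reader of the report being told.

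Two of the three have earlier signals with this drug. Part B of the healthy-volunteer study (Protocol 2.2.4.1) had two DLTs, both also reported as SAEs: "These were 1 elevated lipase (200-mg cohort) and 1 pyrexia (400-mg cohort". In the double-blind period of the ITP study (Protocol 2.2.4.6), treatment-related amylase increase was among the three most frequent terms, at 14.7% versus 0. Exclusion criterion 3 (Protocol 5.1.2) keeps out patients with amylase or lipase above the upper limit of normal. A Grade 3 or 4 value in an eligible patient would therefore be a new rise.

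The pH row raises the opposite risk: a grade with no matching measurement, which could be filled from the wrong specimen.

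**Working it through.** The plan states no figure on this point, so there is none to reproduce. The check sets the grading table against what is collected.

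**Step 1. Rows in SAP Appendix 2.** There are 26: hemoglobin, platelets, neutrophils, lymphocytes, eosinophils, aPTT, INR, albumin, glucose, creatinine, creatine kinase, ALP, AST, ALT, calcium, magnesium, potassium, cholesterol, bilirubin, triglycerides, urine protein, LDH, GGT, urate, pH and leukocytes.

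**Step 2. Compare with Protocol 5.6.9.** Seven analytes from the chemistry panel and the amylase/lipase item have no row: lipase, amylase, sodium, urea, chloride, phosphorus and total protein. This point concerns the first three, on the assumption that CTCAE v5.0 grades them; the documents do not reproduce CTCAE. In the other direction, creatine kinase and GGT have rows but are not in the protocol's chemistry panel. Grading potassium, calcium and magnesium but not sodium, with no reason given, suggests a generic table rather than a decision.

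**Step 3. Trace each analyte to its output.**

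| Analyte | Protocol rule calling for grades | Output under SAP 17.4 as written |
|---|---|---|
| Sodium | 7.3.3.3 (chemistry panel) and synopsis | Descriptive statistics, clinical-significance shift, listing |
| Lipase, amylase | Synopsis only (separate item in 5.6.9) | Descriptive statistics, clinical-significance shift, listing |

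None gets a grade shift or a grade flag.

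**Step 4. Does AE reporting fill the gap?** Only in part. Protocol 6.4.4 records a laboratory abnormality as an AE only if it is clinically significant and needs active management. Its examples are broad and include closer follow-up and further investigation, so many high values will become graded AEs. A high-grade value on which nobody acted will not. The AESI searches in SAP Table 3 have no pancreatic category.

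**Step 5. Apply the pH row to urine.** The documents give no urine range. Assume dipstick steps of 4.5 to 8.5 by 0.5, which is 9 steps.

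- Row read literally: 4.5, 5, 5.5, 6, 6.5 and 7 are below 7.3, so 6 steps are Grade 3 acidosis. 7.5 is Grade 0 or 1. 8 and 8.5 are above 7.5, so 2 steps are Grade 3 alkalosis. In total 6 + 2 = 8 of 9 steps are Grade 3.
- A value must first lie outside the laboratory's normal range: Grade 3 acidosis steps number 0 for a range of 4.5–8.0, 1 for 5–8, 1 for 5–7 and 3 for 6–7.5.
- Urine pH never mapped to the row: 0, and the row is empty.

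The result therefore runs from none to 6 of 9 steps as Grade 3 acidosis, depending on programming choices that the SAP leaves open.

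**The case against.** **Nothing serious is lost.** A reader might infer that the plan would miss a known DLT. The documents do not support that. The lipase DLT occurred in a different study. In this trial, a non-hematologic TEAE of Grade 3 or above in the DLT window counts as a DLT unless it is clearly unrelated or is controlled nausea or vomiting (Protocol 4.4). DLTs have their own eCRF page, are graded, and are tabulated and listed (SAP 17.1). Nor would lipase and amylase be absent from the report, because SAP 17.4 names them for both tables and listings. All of this stands. It limits the gap to laboratory-derived grades.

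**The SAP follows the protocol body.** Protocol 7.3.3.3 confines grade shifts to the hematology and chemistry panels, and lipase and amylase are listed outside them. That is fair for those two analytes, but the synopsis rule and the 4.8.2 outcome are not so confined. Sodium is inside the panel on either reading.

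**The signal is weak.** 14.7% of 34 is 5 patients, against 0 of 11. The two-sided Fisher p-value is (278,256 + 92,565 + 11,220 + 462) / 1,221,759 = 0.31. The treatment-related Grade 3 or higher events listed for that study include neither enzyme, and pancreatic events are not AESIs (Protocol 6.2.3). This tempers the urgency. The outcome in 4.8.2 does not depend on a prior signal.

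**The pointer to Appendix 2 is not worded as exclusive.** True, but the SAP contains no other laboratory grading rule.

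**False acidosis is hypothetical.** No text maps urine pH to the row, and the protein row does say urine, which suggests that unlabelled rows are not urinary. That is reasonable, and it makes an empty row the likelier result. Nothing in the SAP rules the mapping out, though, and urinalysis is among the tests to be tabulated.

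**Conclusion.** The gap is real and of moderate weight; it should be corrected. As written, laboratory-derived Grade 3/4 incidence would not be reported for lipase, amylase or sodium in any of the 48 expansion patients or in the escalation patients. The case is firmest for sodium, which Protocol 7.3.3.3 covers directly. For lipase and amylase it rests on the synopsis rule and the 4.8.2 outcome, and it matters more because of their history with this drug. The amount of information lost cannot be stated in advance: it is the Grade 3/4 values that never became AEs.

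The pH row has no use with scheduled data. A reader might infer that nearly every patient would be reported with Grade 3 acidosis. That needs urine pH to be mapped to the row, no check against the normal range, and a urine pH distribution that the documents do not give. The supported statement is that the row is empty at best and misleading if filled from urinalysis.

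The creatine kinase and GGT rows do not need to go. An unused row distorts nothing, and GGT is named among the raised hepatic enzymes in Protocol 2.3.2.1 and as a treatment-related Grade 3 or higher event in the ITP study.

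The conclusion assumes that CTCAE v5.0 grades the three analytes and that Appendix 2 is the full list of graded parameters.

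**What to change.** In SAP Appendix 2, add rows for serum lipase, serum amylase and sodium (high and low), with criteria taken from the CTCAE v5.0 that the SAP already names. Include them in the grade shift tables and listing flags of SAP 17.4, and report their Grade 3/4 incidence by dose level in Stage 1 and by malignancy type in Stage 2. If the sponsor prefers to leave any of them ungraded, the SAP should say so and give the reason.

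Delete the pH row, or label it as blood pH only and state that urinalysis pH is excluded. Keep the creatine kinase and GGT rows, marked as applying only if collected.

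No new data are needed; the cost is a table edit and programming. The SAP introduction allows revision before final database lock. If the lock has passed, the added tables can be produced and documented as a deviation in the study report.

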## APPENDIX 3. PROGRAMMING CONVENTIONS FOR OUTPUTS

### Dates & Times

Depending on data available, dates and times will take the form yyyy-mm-dd and hh:mm:ss.

